### **Patients:**

Pediatric patients who are expected to require PN for at least 90 consecutive days, both in hospital or home care setting. For patients who remain on PN, treatment will be continued for up to 1 year. Patients will be randomized into one of three age group cohorts:

- 48 patients 3 months to < 2 years of age
- 48 patients 2 years to < 12 years of age
- 48 patients 12 to 16 years of age

## Clinical Study Protocol SMOF-028-CP4 Smoflipid® (lipid injectable emulsion)

---

- Inclusion Criteria:**
1. Male or female patients 3 months to 16 years of age.
  2. Patients who require PN for at least 5 days/week.
  3. Patients who receive 60% or more of their total energy requirements as PN at enrollment and who are expected to receive 60% or more of their total energy requirements as PN for at least 90 days.
  4. Written informed consent from parent(s) or legal representative(s). If possible, patient assent must also be obtained (according to local law).

- Exclusion Criteria:**
1. Known hypersensitivity to fish, egg, soybean, or peanut proteins, or to any of the active ingredients or excipients of Smoflipid or Intralipid 20%.
  2. Hyperlipidemia or disorders of lipid metabolism characterized by hypertriglyceridemia (serum triglyceride concentration > 250 mg/dL).
  3. Inborn errors of amino acid metabolism.
  4. Cardiopulmonary instability (including pulmonary edema, cardiac insufficiency, myocardial infarction, acidosis and hemodynamic instability requiring significant vasopressor support).
  5. Hemophagocytic syndrome.
  6. Liver enzymes (either AST, or ALT, or GGT) exceeding 5 x upper limit of normal range
  7. Direct bilirubin  $\geq$  2.0 mg/dL
  8. INR > 2.
  9. Any known hepatic condition outside of IFALD that will increase direct bilirubin  $\geq$  2.0 mg/dL.
  10. Clinically significant abnormal levels of any serum electrolyte (sodium, potassium, magnesium, calcium, chloride, phosphate).
  11. Active bloodstream infection demonstrated by positive blood culture at screening.
  12. Severe renal failure including patients on renal replacement therapy.
  13. Abnormal blood pH, oxygen saturation, or carbon dioxide.
  14. Pregnancy or lactation.
  15. Participation in another clinical study.
  16. Unlikely to survive longer than 90 days.

**Target Variables:**

Efficacy:

- Body weight (weight velocity as z-score change from baseline).
- Body length/height (growth velocity as z-score change from baseline).

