#### Statistical evaluation:

All target variables will be analyzed in an exploratory manner presenting descriptive statistics. Binary, categorical and ordinal parameters will be summarized by means of absolute and percentage numbers. Numerical data will be summarized by means of standard statistics. Confidence intervals (CI) will be determined for all outcome parameters for which mean and standard deviation will be calculated. The detailed list will be included in the Statistical Analyses Plan (SAP).

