### 5.2 Target Variables

#### Efficacy variables:

- Body weight (weight velocity as z-score change from baseline).
- Body length/height (growth velocity as z-score change from baseline).
- Head circumference for patients who are < 36 months of age (z-score change from baseline).
- Fatty acid profiles including linoleic acid,  $\alpha$ -linolenic acid, arachidonic acid, docosahexaenoic acid, eicosapentaenoic acid, and Mead acid in total plasma (according to Mayo Medical Laboratories standards) and in red blood cell membranes.
- Triene/tetraene ratio (Holman Index) in plasma to assess essential fatty acid deficiency (EFAD). Severity of EFAD will be graded based on triene/tetraene ratio, as suspected  $\geq 0.05$ , moderate  $\geq 0.20$  and severe  $\geq 0.40$  (Cober et al 2012).

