As Smoflipid and its components have been used widely and given world-wide with a very rare incidence of adverse drug reactions (ADRs)/serious adverse events (SAEs), no confirmatory hypotheses will be tested. All target variables will be analyzed in an exploratory manner presenting descriptive statistics. The trial will not be powered. To power this trial, selection of one single parameter would be required as a primary safety endpoint to show a clinically meaningful difference between the treatment groups (the treatment effect) in a reasonable sample size and trial duration. As mentioned above, both Smoflipid and Intralipid 20% provide parenteral lipids. Selecting a single parameter to power the study as a superiority study or as a non-inferiority study with a reasonable non-inferiority margin would be difficult because the similar treatment concept would require more patients than could be obtained under any reasonable circumstances due to very low incidence of adverse drug reactions.

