## **7.2 Statistics**

### **7.2.1 Sample Size Estimation**

Sample size was defined as 144 patients (48 patients 3 months to < 2 years of age, 48 patients 2 years to < 12 years of age, and 48 patients 12 to 16 years of age), having completed Study Day 90. This is to ensure that at least 23 subjects are randomized to each treatment group within each age group.

Based on a presentation at the FDA's Pediatric Clinical Investigators Training in 2014, where it was noted that the minimum of 100 pediatric subjects is required to assess safety (Lewis 2014), the planned patient numbers (24 in each arm within each age group, or 144 total) are adequate to provide sufficient information on safety of pediatric dosing considering the low risk safety profile of Smoflipid in adults. The current study will enroll approximately 72 patients in the investigational group. Additional data for pediatric patients (neonates and infants) receiving Smoflipid will come from the clinical study started in December 2015 in the USA (see Section 4.1).

An exploratory study using descriptive statistical analysis of the target variables will be performed. There is no primary outcome parameter and the study is not powered. Reasons for this study design are explained in Section 6.2.

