### 7.2.3 Statistical Analysis

The study outcome measures were selected in order to assess the safety and nutritional efficacy of the PN lipid emulsion. No primary and secondary measures are defined. Outcome measures will be evaluated as they are documented. Laboratory values will be transformed into SI (Système International d'Unités) if necessary.

A comprehensive Statistical Analysis Plan (SAP), covering details of all methods used to analyze the various parameters will be prepared. It will also include information on the handling of missing values. The SAP will be reviewed, and if needed, updated before data analysis. The SAP will be approved and signed off prior to unblinding the study.

All target variables will be analyzed in an exploratory manner presenting descriptive statistics. Binary, categorical and ordinal parameters will be summarized by means of absolute and percentage numbers (including 'missing data' as valid category). Numerical data will be summarized by means of standard statistics (e.g., number of available data, mean, standard deviation, minimum, median, maximum, and lower and upper quartile). Confidence intervals (CI) will be determined within treatment for all outcome parameters for which mean and standard deviation will be calculated.

Wherever useful, the summary statistics will be presented by Study Day. Results will be presented stratified by study drug and age group, and overall. In addition, appropriate figures (e.g., bar charts, Box-Whisker-Plots) may be presented to summarize the results for some parameters also in a graphical way.

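### Growth efficacy is summarised as raw z-score change with no baseline-adjusted comparison stated, so a chance difference between arms in entry z-score carries into the observed difference

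*Combined protocol and SAP*

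**What the plan says.** The Study outline (Target Variables) and Section 5.2 list three growth outcomes: "Body weight (weight velocity as z-score change from baseline"), "Body length/height (growth velocity as z-score change from baseline") and "Head circumference for patients who are < 36 months of age (z-score change from baseline").

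The analysis is described in the Study outline and Section 7.2.3: "All target variables will be analyzed in an exploratory manner presenting descriptive statistics". Section 7.2.3 adds "Results will be presented stratified by study drug and age group, and overall", and on intervals: "Confidence intervals (CI) will be determined within treatment for all outcome parameters for which mean and standard deviation will be calculated". It names no covariate, no model and no between-arm estimate for growth.

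Section 6.2 says that "no confirmatory hypotheses will be tested", and Section 7.2.1 that "There is no primary outcome parameter and the study is not powered". Section 6.3 randomises 1:1 within three age cohorts and has no other stratification factor. Section 7.2.1 plans 24 per arm per cohort and aims for at least 23.

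The title and Section 5 nevertheless set a comparative objective, Smoflipid against Intralipid 20%. Section 11.2.1 (Baseline documentation) records weight, length or height, and head circumference under 36 months before the first dose. Section 7.2.3 leaves method details to a SAP, to be signed off before unblinding. The supplied text contains no SAP.

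**The concern.** A change score is negatively related to its own baseline whenever baseline and follow-up correlate at less than 1. If one arm of a cohort happens to enrol smaller children, its mean change is expected to be larger even when the two emulsions do equally well. Cohorts of about 24 per arm, balanced on age but not on size, leave room for such gaps.

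With no test and no planned between-arm estimate, readers will judge comparative growth by setting the two arms' mean changes side by side, cohort by cohort. Sections 4.2 and 6.2 say that anthropometry is included at the FDA's request, so these tables will be read. If adjustment is not specified before unblinding, adding it later, once an imbalance is visible, would be a post-hoc choice.

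**Working it through.** **Inputs from the protocol.** Three cohorts of 48, with 24 per arm in each (Section 7.2.1). The counts reproduce: 3 × 48 = 6 × 24 = 144 in total, and 3 × 24 = 72 on Smoflipid. There is no power calculation to reproduce.

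**Assumed inputs (not in the documents).** SD of the z-score s = 1.0 to 1.5, equal at baseline and follow-up. Correlation r = 0.6 to 0.95, the low end for infants over many months and the high end for older children over 90 days.

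**Step 1: size of a chance baseline gap.** The SD of the between-arm difference in mean baseline is s × √(2/n).
- n = 24: √(2/24) = 0.289 s. The chance of a gap above 0.25 s is 39% in a given cohort, so 1 - 0.61³ = 77% in at least one of three. For a gap above 0.5 s the chance is 8%, or 1 - 0.92³ = 22%.
- n = 72: √(2/72) = 0.167 s. The chances are 13% and 0.3%.

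**Step 2: what the gap does to the raw comparison.** With no treatment effect, the expected difference in change, given the gap, is -(1 - r) × gap. For a gap of one SD this is (1 - r) × s × √(2/n):

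| r | n = 24, s = 1.0 | n = 24, s = 1.5 | n = 72, s = 1.0 | n = 72, s = 1.5 |
|---|---|---|---|---|
| 0.6 | 0.115 z | 0.173 z | 0.067 z | 0.100 z |
| 0.8 | 0.058 z | 0.087 z | 0.033 z | 0.050 z |
| 0.95 | 0.014 z | 0.022 z | 0.008 z | 0.013 z |

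**Step 3: the same quantity as variance.** Per child, the change score has variance 2s²(1 - r) and the baseline-adjusted outcome s²(1 - r²). The ratio is (1 + r)/2, so adjustment saves 20% at r = 0.6, 10% at 0.8 and 2.5% at 0.95. Since 2(1 - r) = (1 - r²) + (1 - r)², the saving is exactly the imbalance term of Step 2. At r = 0.6, for example, 0.80 = 0.64 + 0.16, and 0.16/0.80 = 20%. Steps 2 and 3 describe one effect.

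These savings are large-sample values. Estimating the slope inflates the adjusted variance by about 1 + 1/(2n - 4), which is 1 + 1/44 = 1.023 at 24 per arm. Within one cohort at r = 0.95 the ratio becomes 0.975 × 1.023 = 0.997, so almost no gain remains there.

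**Step 4: simulation check.** 100,000 trials, 24 per arm, s = 1, no treatment effect:

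| | r = 0.7 | r = 0.9 |
|---|---|---|
| Mean difference in change, all trials | 0.000 | 0.000 |
| Slope on baseline gap, raw change | -0.30 | -0.10 |
| Slope on baseline gap, ANCOVA | 0.00 | 0.00 |
| Apparent gain of an arm smaller by more than 1 SD of the imbalance (mean gap 0.44 z), raw change | 0.129 z | 0.045 z |
| The same, ANCOVA | -0.003 z | 0.001 z |

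**The case against.** The strongest reply is that nothing here is wrong on average. Allocation is randomised within age cohort, so the raw difference in change is unbiased, as the simulation confirms. A chance gap can favour either arm, and its contribution already lies inside the ordinary standard error of a raw difference. With s = 1.5 and n = 24 that is s × √(2(1 - r)) × √(2/n) = 0.39, 0.27 and 0.14 z at r = 0.6, 0.8 and 0.95. No between-arm growth estimate is planned, no hypothesis is tested, and the SAP may yet supply adjustment. All of this stands, and it limits the point to precision and to the fair reading of one realised trial. It does not remove it: the protocol sets a comparative objective and states only raw change.

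A reader might go further and infer that regression to the mean will make each arm's own change look like nutritional efficacy. The documents do not support that. No criterion in Sections 9.2 or 9.3 selects children on weight, height or z-score. Under the equal-SD model used here, a group enrolled without such selection regresses towards its own population mean, not towards z = 0, so its expected shift is zero. Nor would between-arm adjustment cure a within-arm problem if there were one.

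**Conclusion.** The point holds as a modest, inexpensive gap in specification. The protocol states no baseline-adjusted growth comparison. A one-SD chance imbalance then puts about 0.01 to 0.17 z into the observed difference within a cohort, and about 0.01 to 0.10 z overall. Equivalently, adjustment removes 2.5% to 20% of the variance; these are not two separate harms. The range rests on assumed s and r and on equal SDs at the two visits. The effect is negligible if r is near 0.95 and worth removing if r is nearer 0.6.

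It would be wrong to infer that the planned summaries are biased, that a confirmatory result is at risk, or that the final analysis is known to ignore baseline. The first is contradicted by randomisation and the second by the exploratory design. The third cannot be judged without the SAP.

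**What to change.** Keep the raw change summaries. In Section 7.2.3 and in the SAP, before unblinding:

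1. Tabulate baseline z-scores for weight, length/height and head circumference by arm and age cohort.
2. State that the between-arm difference in z-score at a fixed visit, for example Day 90, will also be estimated by ANCOVA adjusted for baseline z-score and age cohort (baseline only, within a single cohort). Report it with its confidence interval, as a descriptive estimate and without a hypothesis test. Using follow-up z-score or change as the outcome gives the same treatment difference.

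A breakdown of change by baseline z-score band is not recommended. It selects on baseline, which itself produces regression to the mean in the outer bands, and it would split about 24 children several ways.

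The cost is a few lines of text, one baseline table and one extra estimate per growth outcome, all from data already collected. No added patients, visits or tests are needed.

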## Clinical Study Protocol SMOF-028-CP4

### Smoflipid® (lipid injectable emulsion)

---

- Head circumference (patients < 36 months of age [z-score change from baseline]).
- Fatty acid profiles including linoleic acid,  $\alpha$ -linolenic acid, arachidonic acid, docosahexaenoic acid, eicosapentaenoic acid and Mead acid, analyzed in total plasma and in red blood cell membranes.
- Triene/tetraene ratio (Holman Index) in total plasma to assess essential fatty acid deficiency (EFAD).

#### Safety:

- Incidence of PNALD/PNAC: Number of patients in each treatment group with direct bilirubin levels > 2 mg/dL, confirmed by a second sample collected 7 days after the first sample (incidence of PNALD/PNAC).
- Time from Study Day 1 until reaching direct bilirubin levels > 2 mg/dL, followed up by a second sample collected 7 days after the first sample (time until developing PNALD/PNAC).
- Sterols in plasma including phytosterols:  $\beta$ -sitosterol, campesterol, stigmasterol, brassicasterol, ergosterol, cholesterol, desmosterol, lanosterol,  $\beta$ -sitostanol, lathosterol, squalene (a sterol precursor).
- Laboratory values (blood, plasma, or serum): triglycerides, direct bilirubin, total bilirubin, alanine aminotransferase (ALT), aspartate aminotransferase (AST), gamma-glutamyl transferase (GGT), alkaline phosphatase (ALP), creatinine, urea nitrogen, electrolytes (Na, K, Mg, Cl, Ca, Phosphate), trace elements (ferritin, Zn, Se, Cu, Mn, Cr), glucose, total protein, C-reactive protein (CRP), white blood cells (WBC), red blood cells (RBC), and platelet counts, hemoglobin (hgb), hematocrit (hct), international normalized ratio (INR).
- Vital signs: blood pressure, heart rate, body temperature.
- All adverse events (AEs).
- The relation between genetic polymorphisms in the fatty acid desaturase genes FADS1 and FADS2 and plasma concentrations of linoleic acid,  $\alpha$ -linolenic acid, arachidonic acid, docosahexaenoic acid, eicosapentaenoic acid, and Mead acid, as well as relation to EFAD (triene/tetraene ratio).

---

 In this study protocol, the terms PNAC and PNALD are used synonymously and are defined by direct bilirubin levels > 2 mg/dL.

## Clinical Study Protocol SMOF-028-CP4 Smoflipid® (lipid injectable emulsion)

---

### Statistics:

#### Sample Size:

Defined as 144 patients (48 patients per age group cohort), having completed Study Day 90 to ensure that at least 23 subjects are randomized to each treatment group within each age group cohort.

#### Statistical evaluation:

All target variables will be analyzed in an exploratory manner presenting descriptive statistics. Binary, categorical and ordinal parameters will be summarized by means of absolute and percentage numbers. Numerical data will be summarized by means of standard statistics. Confidence intervals (CI) will be determined for all outcome parameters for which mean and standard deviation will be calculated. The detailed list will be included in the Statistical Analyses Plan (SAP).

#### Analysis sets:

*Safety population:* all patients having received at least one dose of a study drug and at least one post-baseline safety evaluation – used for analysis of safety variables.

*Intention-to-treat (ITT) population:* all randomized patients.

*Per-protocol (PP) population:* all randomized patients having received study drug at least until Study Day 90, with 5 to 7 infusions per week, and without any major protocol deviations. ITT and PP populations will be used for analysis of efficacy variables.

### Evaluations/Follow up:

All data will be collected according to the study schedule (see Section 1).

After obtaining a signed and dated informed consent form (ICF) and before administering the first dose of study drug, baseline assessments will be completed including:

- Review of inclusion and exclusion criteria. Eligibility of a patient can be assessed from existing laboratory data if the data are not older than one week.
- Collection of demographic data.
- Recording the patient's medical history, vital signs, physical examination, nutritional status (anthropometric: head circumference [ $< 3$  years]) length [ $< 2$  years], height, weight, BMI (body mass index) [ $> 2$  years]), concomitant medications, duration and composition of current PN.
- After patient eligibility is confirmed, baseline blood samples will be withdrawn for analyses of safety and efficacy laboratory parameters.

**Clinical Study Protocol SMOF-028-CP4**  
**Smoflipid® (lipid injectable emulsion)**

---

Once the ICF is signed and dated, AEs will be documented throughout the study and followed after receiving the first dose of treatment until resolved.

Study Day 1 is the day on which the first administration of the study drug starts. Baseline assessments are performed, and the patient is randomized, earlier on the same day. Alternatively, baseline assessments and randomization can be performed on study Day -1, i.e., the day before Day 1. Home care patients will stay overnight in the hospital for the first study drug infusion and can leave on Day 2. Alternatively, home care patients that are stable on home parenteral nutrition (HPN) prior to study participation can also be trained and receive the first dose of study treatment at the hospital, returning to their home on the same day (Day 1).

Volumes of administered study drugs, brands and volumes of administered parenteral amino acids and dextrose and, if applicable, brands and volumes administered of enteral formulas, volumes of human milk or milk formulas, and as far as possible, type and amount of ingested oral food, will be documented for each Study Day.

Blood samples for safety and efficacy laboratory analysis, analyses of fatty acids and sterols will be taken monthly. Samples for trace elements will be taken every 3 months (see 1. Study Schedule). All blood samples will be taken at the hospital during the monthly visit. Other measurements and examinations will be performed monthly as well during the hospital visits. One blood sample is taken during the treatment phase for genetic analysis (FADS1, FADS2) (see 1. Study Schedule).

After cessation of the last infusion of study drug, a Final Study Visit will be performed (see 1. Study Schedule).

**Clinical Study Protocol SMOF-028-CP4**  
**Smoflipid® (lipid injectable emulsion)**

---

**Other Investigators/Sites:** ■ sites are planned, all in the USA

**Final Protocol**

**Submission to FDA:** ■■■■■■■■■■

**Clinical Study Protocol SMOF-028-CP4**  
**Smoflipid® (lipid injectable emulsion)**

**1. Study Schedule**

**Daily procedures and assessments during treatment phase (starting on Day 1):**

Study drug administration, study drug administered, other PN products administered, EN administered and oral food intake, adverse events, concomitant medication.

**Table 1: Study Schedule of Assessments and Procedures**

Assessments/ Procedures	Study Days	Screening / Baseline Visit Prior to Start of PN with Study Drugs	Treatment Phase Study Drug Administration Day 1 to Day 365 §			Final Study Visit / After End of Last Study PN
		Day 1 or Day -1 *	Day 1 Visit *	Weekly Call (± 1 day)	Monthly Visit (± 5 days)	Every 3 months, (during a monthly visit)
Informed consent		X				
Inclusion/exclusion criteria		X				
Demographics incl. race and ethnicity		X				
Pregnancy test, if applicable		X				
Randomization		X				
Medical history, demographic data		X				
Prior/concomitant medication		X			X	X
Body weight, length/height, head circumference		X			X	X
Physical examination incl. Tanner stage		X			X	X
Vital signs a		X			X	X
Blood sampling for standard laboratory b		X			X	X
Blood sampling for special laboratory c		X			X	X
Blood sampling for trace element analysis d		X				X
Start of study drug infusion			X			
Prior / concomitant nutrition e		X		X		X
Adverse events f		X	X	X	X	X
Blood sampling for genetic analysis (FADS1, FADS2) g					(X)	

\* Screening, baseline assessments and randomization are performed on Day 1, prior to the start infusion of study PN, or alternatively on Day -1, i.e., the day before Day 1. Study drug infusion starts on Day 1.

\*\* One day after last day of study drug administration.

§ During the treatment phase, study drug will be administered 5 to 7 days per week. A break of 1 or 2 days per week is allowed and will not lead to prolongation of the treatment phase.

a Blood pressure, heart rate, body temperature.

b Triglycerides, direct bilirubin, total bilirubin, ALT, AST, GGT, ALP, creatinine, urea nitrogen, electrolytes (Na, K, Mg, Cl, Ca, Phosphate), glucose, total protein, CRP, WBC, RBC, and platelet counts, hgb, hct, INR.

c Fatty acid profiles (linoleic acid,  $\alpha$ -linolenic acid, arachidonic acid, docosahexaenoic acid, eicosapentaenoic acid and Mead acid, analyzed in total plasma, and in red blood cell membranes);

